3.2 Inclusion Criteria

Subject must meet the following criteria for inclusion in this study:

Signed Written Informed Consent

- 1) Voluntarily signed and dated Institutional Review Board (IRB)/ Ethics Committee approved informed consent form in accordance with regulatory and institutional guidelines. Written informed consent must be obtained prior to performing any study-related procedure;

Age and Sex

- 2) Males and female subjects ≥ 18 years of age at the Pre-treatment Visit, i.e., at the time that written informed consent is obtained, except in Japan where subjects must be ≥ 20 years of age;

Target Population

- 3) Histologically confirmed diagnosis of MF or SS;
 - a. For SS (defined as meeting T4 plus B2 criteria), where the biopsy of erythrodermic skin may only reveal suggestive but not diagnostic histopathologic features, the diagnosis may be based on either a node biopsy or fulfillment of B2 criteria including a clone in the blood that matches that of the skin (Olsen, 2011).
- 4) Stage IB, II-A, II-B, III and IV (Olsen, 2011) (see [Appendix 1](#));
- 5) Subjects who have failed at least one prior course of systemic therapy (e.g., interferon, denileukin diftitox, bexarotene, photopheresis, anti-neoplastic chemotherapy, etc.). Psoralen plus ultraviolet light therapy (PUVA) is not considered to be a systemic therapy;
- 6) Eastern Cooperative Oncology Group (ECOG) performance status score (Oken, 1982) of ≤ 1 (see [Appendix 2](#)).
- 7) The subject has resolution of all clinically significant toxic effects of prior cancer therapy to Grade ≤ 1 by the National Cancer Institute Common Terminology

Criteria for Adverse Events, version 4.0 (NCI-CTCAE, v.4.0) excluding the specifications required in 8, 9 and 10 below.

- 8) Adequate hematological function:
 - a. absolute neutrophil count (ANC) $\geq 1,500$ cells/ μL ($\geq 1,500/\text{mm}^3$);
 - b. platelets $\geq 100,000$ cells/ μL ($\geq 100,000/\text{mm}^3$);
 - c. in subjects with known bone marrow involvement, ANC must be $\geq 1,000$ cells/ μL ($\geq 1,000/\text{mm}^3$) and platelets $\geq 75,000$ cells/ μL ($\geq 75,000/\text{mm}^3$).
- 9) Adequate hepatic function:
 - a. bilirubin ≤ 1.5 times the specific institutional upper limit of normal (ULN), except for subjects with Gilbert's syndrome;
 - b. aspartate transaminase (AST) and alanine transaminase (ALT) each $\leq 2.5 \times \text{ULN}$ or $\leq 5.0 \times \text{ULN}$ in the presence of known hepatic involvement by CTCL.

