5 TREATMENT PLAN

5.1 Assignment to Study

After a subject signs consent, screening numbers should be assigned by the investigator (or designee) using ClinTrak Interactive Voice/Web Response System (CTIVRS). Once assigned, numbers for any screen failures or non-treated, non-evaluable, or discontinued subjects will not be re-used.

A subject who meets all entry criteria will be randomized in a 1:1 ratio to receive KW-0761 or vorinostat. The randomization to treatment groups will be stratified by disease type (MF or SS) and disease stage (IB/II or III/IV). When a subject is determined to be eligible for randomization the investigator (or designee) will contact CTIVRS to obtain the randomization assignment for the subject. If a subject is randomized in error, or a dosing error occurs, KKD (or designee) should be notified as soon as the error is discovered.

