6.11.2.6 Adjustment for Covariates

Additional analysis of the treatment effect on PFS and ORR as assessed by the Investigator when adjusted for potential prognostic factors will be carried out using a multivariate Cox proportional hazard model for PFS and a multivariate logistic regression model for ORR. These analyses will be performed based on the PFS and ORR as assessed by the Investigator for the first assigned therapy and the ITT Set. Potential prognostic factors including disease

type (MF or SS), disease stage (IB and II versus III or IV), compartment involvement (blood involvement or no blood involvement), region (US, Japan, Rest of World), age group (<65 or ≥65 years), gender (males or females), and race category (Black or African American, White, Other) will be included as covariates in the multivariate Cox proportional hazard model for PFS and the multivariate logistic regression model for ORR. Backward selection will be used to identify the final set of prognostic factors (exit p-value is set to be 0.1). The final model will then be used to assess treatment effect when adjusted for these important prognostic factors.

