Note: Hazard ratio, 95% CI, and p-value are obtained from a Cox proportional hazard model with treatment, disease type, disease stage, Blood Involvement, region, age group, gender, and race category as explanatory variables.

<<Programming Note: Backward selection method will be used to identify the final set of prognostic factors (exit p-value is set to be 0.1).
 Treatment will be fixed in the model, i.e., will not be eliminated.>>

The following table will have a similar layout as Table 14.2.1.1:

Table 14.2.1.6.1
Summary of Progression-Free Survival (PFS)
Efficacy Evaluable Set

Table 14.2.1.6.2
 Summary of Progression-Free Survival (PFS)
 Intent-to-Treat Set
 Any Exposure to KW-0761 vs. Vorinostat Only

	KW-0761#			
	Vorinostat N=xxx	Crossover	Randomized to KW-0761 N=xxx	Any KW-0761
By Investigator's Assessment				
Number of Subjects with PFS Event (n, %)	xx (xx.x)	xx (xx.x)	xx (xx.x)	xx (xx.x)
Earliest Contributing Event:				
Progressive Disease	xx (xx.x)	xx (xx.x)	xx (xx.x)	xx (xx.x)
Death	xx (xx.x)	xx (xx.x)	xx (xx.x)	xx (xx.x)
Number of Subjects Censored (n, %)	xx (xx.x)	xx (xx.x)	xx (xx.x)	xx (xx.x)
Progression-Free Survival (months)				
Kaplan-Meier Estimate of PFS				
Q1	xx.x	xx.x	xx.x	xx.x
Median (95% CI)*	xx.x (xx.x, xx.x)	xx.x (xx.x, xx.x)	xx.x (xx.x, xx.x)	xx.x (xx.x, xx.x)
Q3	xx.x	xx.x	xx.x	xx.x
Mean	xx.xx	xx.xx	xx.xx	xx.xx
Standard Deviation	xx.xxx	xx.xxx	xx.xxx	xx.xxx
Median	xx.xx	xx.xx	xx.xx	xx.xx
Minimum	xx.x	xx.x	xx.x	xx.x
Maximum	xx.x	xx.x	xx.x	xx.x
----- Treatment Comparison -----				
KW-0761 vs. Vorinostat**				
Hazard Ratio (95% CI)				xx.x (xx.x, xx.x)
Log rank p-value				x.xxxxx
Rate (%) of Being Alive without Progression for at Least***				
6 months (95% CI)	xx.x (xx.x, xx.x)	xx.x (xx.x, xx.x)	xx.x (xx.x, xx.x)	xx.x (xx.x, xx.x)
12 months (95% CI)	xx.x (xx.x, xx.x)	xx.x (xx.x, xx.x)	xx.x (xx.x, xx.x)	xx.x (xx.x, xx.x)
18 months (95% CI)	xx.x (xx.x, xx.x)	xx.x (xx.x, xx.x)	xx.x (xx.x, xx.x)	xx.x (xx.x, xx.x)
24 months (95% CI)	xx.x (xx.x, xx.x)	xx.x (xx.x, xx.x)	xx.x (xx.x, xx.x)	xx.x (xx.x, xx.x)
Etc.				

Note: Percentage is calculated using the number of subjects in the column heading as the denominator.

* 95% CIs are obtained from SAS proc lifetest using loglog transformation.

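### Backward elimination in the supportive PFS and ORR models can remove disease type, stage and region, and it contradicts the footnotes of both result tables

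*SAP*

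**What the plan says.** SAP 6.11.2.6 describes an additional analysis of the treatment effect on investigator-assessed PFS and ORR in the ITT Set. The candidates are disease type, disease stage, blood involvement, region, age group, gender and race category. The rule for both models is: "Backward selection will be used to identify the final set of prognostic factors", with an exit p-value of 0.1. The reduced model is the one that counts: "The final model will then be used to assess treatment effect when adjusted for these important prognostic factors".

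The programming notes under the shells of Table 14.2.1.5 (PFS) and Table 14.2.2.1.2 (ORR) repeat the rule and protect one term: "Treatment will be fixed in the model, i.e., will not be eliminated". The footnote above the PFS note says instead that the estimates are "obtained from a Cox proportional hazard model with treatment, disease type, disease stage, Blood Involvement, region, age group, gender, and race category". The ORR footnote says the same of the logistic model. Both shells print rows for every factor.

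Protocol 5.1 sets the design factors: "The randomization to treatment groups will be stratified by disease type (MF or SS) and disease stage (IB/II or III/IV". Region is not a randomization factor. SAP 6.11.2.1 nevertheless puts type, stage and region into both the stratified log-rank test and the primary Cox model, and SAP 6.11.2.3 adjusts the CMH test for ORR by the same three.

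**The concern.** An analysis offered as better adjusted than the primary one may end up adjusting for fewer of the design factors. Type, stage and region are fixed in the primary PFS model and in the ORR test, but here each stays only if its p-value in these data is 0.1 or less. A hazard or odds ratio is conditional on the covariates kept, so the data partly choose the quantity reported.

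The second problem is documentary. Each shell tells the reader that all factors were in the model and tells the programmer to remove some. At stake are the clarity and traceability of two supportive tables, not the trial's main conclusion.

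**Working it through.** **1. Which terms are guaranteed to stay**

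- Primary PFS Cox model (SAP 6.11.2.1): treatment, type, stage, region.
- ORR CMH test (SAP 6.11.2.3): stratified by type, stage, region.
- Adjusted PFS and ORR models (SAP 6.11.2.6 with the programming notes): treatment only.
- Footnotes of Tables 14.2.1.5 and 14.2.2.1.2: treatment and all seven factors. This is true only if nothing is eliminated.

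**2. The plan's event count**

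Inputs from Protocol 10.3: medians 169 and 254 days, one-sided 0.025, 90% power, 1:1 allocation. HR = 169/254 = 0.665.

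Schoenfeld: 4(1.960 + 1.282)² / (ln 0.665)² gives 254 events. Freedman's formula gives 261. Power at 255 events is 90.2%. The planned 255 is reproduced.

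**3. Capacity for PFS**

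Parameters: treatment 1 + type 1 + stage 1 + blood 1 + region 2 + age 1 + gender 1 + race 2 = 10.

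- 255/10 = 25.5 events per parameter.
- If the time cap stops the trial at 191 events (the 80% power row of Protocol Table 10.3-1): 191/10 = 19.1.

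The full model is affordable either way.

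**4. Capacity for ORR**

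The limiting count here is responders, and the documents give no assumed rate. With N = 317 and the same 10 parameters, for assumed pooled rates:

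| Pooled ORR (assumed) | Responders per parameter |
|---|---|
| 10% | 3.2 |
| 20% | 6.3 |
| 30% | 9.5 |
| 40% | 12.7 |

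Ten per parameter, a conventional yardstick, needs 100/317, a pooled ORR of about 32% (100/288, about 35%, at N = 288). A model with treatment 1 + type 1 + stage 1 + region 2 = 5 parameters needs 50/317, about 16%.

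**5. Can a real prognostic factor be eliminated?**

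For one binary factor taken alone, with prevalence a, D events and true hazard ratio h: z = √(D·a(1−a))·|ln h|, and P(eliminated) = Φ(1.645 − z) − Φ(−1.645 − z).

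Example with D = 255, a = 0.5 (assumed), h = 1.2: z = 7.98 × 0.182 = 1.46, so P is about 57%. On the same assumptions P is 90% at h = 1.0, 80% at 1.1, 33% at 1.3 and 6% at 1.5. With a = 0.15 and h = 1.3 it is 56%.

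Overlap between candidates adds to this for disease type. Protocol 3.2 reads "For SS (defined as meeting T4 plus B2 criteria", so every SS subject has blood involvement. With SS share s and blood-involvement share b, the correlation is √[s(1−b)/((1−s)b)]. For assumed s of 30–60% and b of 60–80% (b above s) it is 0.33–0.80, a variance inflation of 1.1–2.8. The full model tolerates that, but it makes type easier to drop.

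**6. Effect on the PFS treatment estimate**

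A small simulation used 60 trials per scenario, N = 317, an assumed 45% SS, SS implying blood involvement and advanced stage, and assumed hazard ratios of about 1.2 for type and 1.35 for stage. Type was dropped in 53–65% of trials and stage in 32–33%. The average treatment HR was 0.648 (full) against 0.650 (selected) under the design effect, and 1.00 against 0.99 under no effect. Rejection rates were identical. The last trial of each scenario had 273 and 287 events, somewhat more than 255.

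A second set (400 trials per scenario, 255 events, 40% SS assumed, log-hazard effects 0–0.5) gave an average difference in HR of 1.6% and at most 9%, with similar coverage and power. The ORR model was not simulated.

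**The case against.** The strongest reply is that nothing important depends on these models. The effect adjusted for type, stage and region is already reported, by the primary Cox model for PFS and the CMH test for ORR. The section is labelled additional and carries no alpha. The algorithm is fully specified in advance: candidates, exit level, treatment fixed. When type is dropped, the correlated blood term can carry much of its information, and the simulations show almost no movement in the PFS estimate. The tables are mock shells with the selection instruction directly under the footnote. All of this stands, and it sets the size of the point. It does not remove the contradiction inside each shell, and it gives no reason to let design factors leave a PFS model that can hold every term.

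A reader might infer more than the documents support:

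- **That 255 events also justify the full ORR model.** They are PFS events. Responders limit that model, and no response rate is assumed.
- **That loss of a randomization factor is likely.** The second set of simulations dropped at least one in 29–92% of trials, but its range includes zero true effects, where removal occurs about 90% of the time by construction and does no harm. The SS share is not in the documents. Overlap of SS with blood involvement is documented; overlap with advanced stage was assumed, because the staging table in Protocol Appendix 1 is not reproduced in the available text.
- **That the adjusted intervals are unreliable.** Intervals after selection ignore the selection in principle, but simulated coverage was similar.
- **That different covariates for PFS and ORR are a fault.** They need not be, and the fix below also uses different sets.

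**Conclusion.** The concern holds as a minor one. Under SAP 6.11.2.6 and its programming notes, disease type, disease stage and region can be eliminated from both adjusted models, although the main PFS and ORR analyses keep all three. The footnotes of Tables 14.2.1.5 and 14.2.2.1.2 contradict the programming notes and are wrong whenever a factor is removed. These findings rest on the text alone.

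For PFS, selection solves no problem: 25.5 events per parameter, or 19.1 at 191 events. For ORR the full model may be too large, but whether it is depends on a response rate that the documents do not give. How often a factor would be dropped depends on assumed prevalences and effects. The small effect on the treatment estimate was shown by simulation for PFS only, under assumed inputs. The primary analysis is not affected.

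**What to change.** In SAP 6.11.2.6, delete the backward-selection sentence and the following sentence that relies on a selected model. Delete the programming notes on selection under Tables 14.2.1.5 and 14.2.2.1.2.

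- **PFS:** report the full pre-specified model with treatment and all seven factors. The Table 14.2.1.5 footnote and rows already fit it.
- **ORR:** specify now one fixed logistic model with treatment, disease type, disease stage and region, matching the CMH test. Limit the seven-factor list in 6.11.2.6 to PFS. Change the Table 14.2.2.1.2 footnote, and remove its rows for blood involvement, age, gender and race. Fixing the set now avoids a later judgement on whether responders are too few.

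The cost is a few text edits and, for ORR, fewer covariates reported. No data collection, sample size or primary analysis changes.

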6.11.2.7 Subgroup Analyses

Subgroup analyses will be performed for PFS as assessed by the Investigator based on the first assigned therapy for the ITT Set and the Efficacy Evaluable Set provided that there are adequate sample sizes in the respective groups. The following subgroup factors will be used:

- Disease type (MF or SS);
- Disease stage (IB and II versus III or IV);
- Blood involvement (yes or no);
- Region (US, Japan, Rest of World);
- Age group (<65 years or ≥65 years);
- Gender (male or female);
- Race category (Black or African American, White, Other).
- LDH (normal versus elevated)

Forest plot of hazard ratios by subgroups will be provided for PFS as assessed by the Investigator. Additional subgroup analyses may be performed.

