Comparisons between treatment arms for all other secondary endpoints such as Likert scale, and Itchy QoL will be conducted with no adjustment for multiple comparisons used for those statistical tests. Exploratory subset analyses for PFS and any of the secondary endpoints by region, study site, compartment involvement, CCR4 expression status, disease subtypes, and medical history may be conducted. Details of such subset analyses will be provided in the Statistical Analysis Plan. Although overall survival (OS) is not a secondary endpoint, each subject will be followed in this study for a minimum of 2 years to generate information on OS. Using this follow-up information, a comparison between treatment arms for OS will also be conducted and considered exploratory. Statistical analyses on OS using follow-up data may take place after database lock for the study and will be reported as supplemental to the Clinical Study Report.

Randomization will be stratified within the 2 disease types, SS and MF and 2 disease stages IB or II and III or IV. The efficacy analyses described in this section will be conducted as stratified tests but may also be conducted as a subset analysis within each of these disease-type groups and disease stages. Comparison of endpoints between these 2 groups and

stages will be conducted for each treatment assuming adequate sample sizes in the respective groups.

Exploratory analyses based on other subject groupings and with other parameters may also be conducted.

Since the primary endpoint is PFS, the reference median PFS for vorinostat is assumed to be 169 days. The median PFS for KW-0761 therapy is targeted for 254 days, a 50% improvement over this reference median. For a 24-month accrual and 12 month follow-up on the last subject dosed, [Table 10.3-1](#) gives the power and the number of PFS events required to show superior PFS for KW-0761 therapy over vorinostat at the one-sided 0.025 significance level. The ITT set is used for this primary analysis. The same analysis conducted using the Efficacy Evaluable set is considered secondary.

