3.2 Treatment Plan

3.2.1 Assignment to Study

After a subject signs consent, screening numbers should be assigned by the Investigator (or designee) using ClinTrak Interactive Voice/Web Response System (CTIVRS). Once assigned, numbers for any screen failures or non-treated, non-evaluable, or discontinued subjects will not be re-used.

A subject who meets all entry criteria will be randomized in a 1:1 ratio to receive KW-0761 or vorinostat. The randomization to treatment groups will be stratified by disease type (MF or SS) and disease stage (IB/II or III/IV). When a subject is determined to be eligible for randomization the Investigator (or designee) will contact CTIVRS to obtain the randomization assignment for the subject.

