6.3 Determination of Sample Size

Since the primary endpoint is PFS, the reference median PFS for vorinostat is assumed to be 169 days.⁵ The median PFS for KW-0761 therapy is targeted for 254 days, a 50% improvement over this reference median. For a 24-month accrual and 12 month follow-up on the last subject dosed, Table 10.3-1 of the protocol gives the power and the number of PFS events required to show superior PFS for KW-0761 therapy over vorinostat at the one-sided

0.025 significance level. The Intent-to-Treat (ITT) set is used for this primary analysis. The same analysis conducted using the Efficacy Evaluable set is considered secondary.

Under these assumptions, for the ITT population, a total of 255 PFS events will give 90% power. For this study, the final primary analysis comparing PFS between treatment groups will not be conducted until 255 PFS events occur or until a maximum of 24 months after the last randomized subject's first dose, whichever comes first. In the event that the study is stopped prior to 255 PFS events being observed, the primary test will be performed at less than 90% power under the current assumptions according to Table 10.3-1 in the protocol.

Each of these calculations used a log-rank test to compare the two survival curves. Sample size calculations were computed using SAS software version 9.3 using PROC POWER, Twosamplesurvival test = logrank.

The total sample size of 288 represents the approximate number of subjects that may be necessary for 255 PFS events to occur within the projected 36 months of the trial. If a 10% inflation factor is applied to this total (about 29 subjects) to take into account those subjects that may be lost to follow-up prior to documented progression, a total of 317 enrolled subjects may be necessary in order to observe 255 PFS events.

The observed rates of PFS events, recruitment, and drop-outs will be monitored throughout the study and may be used to alter the number of sites, the accrual period, and the follow-up period to achieve the required 255 PFS events in a timely manner. If the 255 PFS events are not observed within 36 months from the start of enrollment the study will be stopped at approximately 24 months after the last randomized subject's first dose.

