6.11.2 Efficacy Analysis Methodology

6.11.2.1 Analysis of Primary Efficacy Variable

The primary comparison of progression-free survival between KW-0761 and vorinostat will be performed on the ITT set based upon the results of the on-site Investigator's assessment using a stratified Log-rank test at the one-sided 2.5% significance level. Stratification is done by disease type (MF or SS), disease stage (IB/II or III/ IV), and region (U.S., Japan, and Rest of World). A Cox proportional hazard model with treatment, disease type, disease stage, and region (U.S., Japan, and Rest of World) as covariates will be used to assess the magnitude of the treatment difference in PFS. The hazard ratio along with the 95% confidence interval obtained from the Cox proportional hazard model will be presented. Additional analyses may be performed adjusting for treatment and other baseline characteristics.

The median PFS and the 2-sided 95% confidence interval for each treatment will be estimated using the Kaplan-Meier survival analysis methods. Kaplan-Meier estimate of PFS rates and the corresponding 95% confidence interval will also be provided for each treatment arm by 6 months intervals. Plots of the Kaplan-Meier estimate of the survival distribution function over time for PFS will be presented by treatment arm.

The primary analysis of PFS will be performed when 255 total PFS events have been observed or 24 months after the last randomized subject's first dose, whichever comes first.

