*** Kaplan-Meier estimate.

For subjects who had KW-0761 treatment, PFS is calculated from the first dose of KW-0761.

Table 14.2.1.7.1
 Summary of Progression-Free Survival (PFS) Based on Investigator's Assessment
 Intent-to-Treat Set
 By Pre-defined Subgroups

Disease Type = MF

	Vorinostat N=xxx	KW-0761 N=xxx
Number of Subjects with PFS Event (n, %)	xx (xx.x)	xx (xx.x)
Earliest Contributing Event:		
Progressive Disease	xx (xx.x)	xx (xx.x)
Death	xx (xx.x)	xx (xx.x)
Number of Subjects Censored (n, %)	xx (xx.x)	xx (xx.x)
Progression-Free Survival (months)		
Kaplan-Meier Estimate of PFS		
Q1	xx.x	xx.x
Median (95% CI)*	xx.x (xx.x, xx.x)	xx.x (xx.x, xx.x)
Q3	xx.x	xx.x
----- Treatment Comparison -----		
KW-0761 vs. Vorinostat**		
Hazard Ratio (95% CI)		xx.x (xx.x, xx.x)
Log rank p-value		x.xxxxx

Note: Percentage is calculated using the number of subjects in the column heading as the denominator.

* 95% CIs are obtained from SAS proc lifetest using loglog transformation.

** Hazard ratio and 95% CI are based on Cox proportional hazards model with treatment, disease stage, and region as covariates. P-value is obtained from a stratified log rank test with disease stage and region as stratification factors.

<<Programming Note: Repeat for the following subgroups: Disease Type (SS), Disease Stage, Blood Involvement, Region, Age group, Gender, Race Category, and Baseline LDH.>>

The following table will have a similar layout as Table 14.2.1.7.1:

Table 14.2.1.7.2
Summary of Progression-Free Survival (PFS) Based on Investigator's Assessment
Efficacy Evaluable Set
By Pre-defined Subgroups

Table 14.2.1.8
 Summary of Progression-Free Survival (PFS) Based on Independent Review
 Intent-to-Treat Set

	Vorinostat N=xxx	KW-0761 N=xxx
Number of Subjects with PFS Event (n, %)	xx (xx.x)	xx (xx.x)
Earliest Contributing Event:		
Progressive Disease	xx (xx.x)	xx (xx.x)
Death	xx (xx.x)	xx (xx.x)
Number of Subjects Censored (n, %)	xx (xx.x)	xx (xx.x)
Progression-Free Survival (months)		
Kaplan-Meier Estimate of PFS		
Q1	xx.x	xx.x
Median (95% CI)*	xx.x (xx.x, xx.x)	xx.x (xx.x, xx.x)
Q3	xx.x	xx.x
Mean	xx.xx	xx.xx
Standard Deviation	xx.xxx	xx.xxx
Median	xx.xx	xx.xx
Minimum	xx.x	xx.x
Maximum	xx.x	xx.x
----- Treatment Comparison -----		
KW-0761 vs. Vorinostat**		
Hazard Ratio (95% CI)		xx.x (xx.x, xx.x)
Log rank p-value		x.xxxxx
Rate (%) of Being Alive without Progression for at Least***		
6 months (95% CI)	xx.x (xx.x, xx.x)	xx.x (xx.x, xx.x)

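### PFS subgroup tables print a separate p-value in up to 18 subgroups, with no test or estimate of whether the treatment effect differs between them

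*SAP*

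**What the plan says.** SAP 6.11.2.7 plans PFS subgroup analyses in the ITT and Efficacy Evaluable sets, provided the groups are large enough; it gives no size threshold. The factors are disease type, disease stage, blood involvement, region, age group, gender, race category and LDH. The display it names is a forest plot: "Forest plot of hazard ratios by subgroups will be provided for PFS as assessed by the Investigator".

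The p-values come from the table shells. Table 14.2.1.7.1 prints an HR with 95% CI and a log-rank p-value in each subgroup panel. The footnote to the MF panel reads "P-value is obtained from a stratified log rank test with disease stage and region as stratification factors", and a programming note repeats the panel for every other subgroup. Table 14.2.1.7.2 does the same for the Efficacy Evaluable set. The note under forest plot 14.2.5 describes a separate Cox model in each subgroup with treatment as the covariate, and names only the HR and CI.

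Protocol 10.3 calls its subset analyses exploratory. It also plans to compare endpoints between the two disease types and between stages; these comparisons of groups and "stages will be conducted for each treatment assuming adequate sample sizes in the respective groups".

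**The concern.** A reader turns to subgroup tables to ask whether the effect differs between levels of a factor: MF and SS, early and late stage, blood involvement or none. Two separate p-values do not answer that. One can fall below 0.05 and the other above it with the same true effect in both, because each level has only part of the events.

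Nothing else in the plan fills the gap. The protocol's comparison within each treatment describes prognosis. The multivariate Cox model in SAP 6.11.2.6 lists main effects only. The SAP's interaction terms (time-by-treatment and treatment-by-baseline, section 6.11.2.3) belong to the quality-of-life models. At stake is a uniform benefit that appears to be absent in some groups.

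**Working it through.** **Inputs from the documents**
- Medians (SAP 6.3): "the reference median PFS for vorinostat is assumed to be 169 days" and "The median PFS for KW-0761 therapy is targeted for 254 days". HR = 169/254 = 0.665; ln(254/169) = 0.4074.
- Events and power (SAP 6.3): "a total of 255 PFS events will give 90% power".
- Test level (SAP 6.11.2.1): "using a stratified Log-rank test at the one-sided 2.5% significance level", equivalent to two-sided 0.05.
- Allocation (SAP 3.2.1): 1:1.
- Subgroups (SAP 6.11.2.7): six two-level and two three-level factors, 6×2 + 2×3 = 18 levels.

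**Assumptions.** The documents give neither subgroup prevalences nor a significance level for subgroups. I use a range of splits, and p<0.05 two-sided in favour of KW-0761. Events are taken to divide in proportion to the split.

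**The plan's own figure.** Schoenfeld's formula for 90% power at one-sided 0.025 gives 254 events (Freedman's gives 261). Power at 255 events is 90.2%. The planned 255 is reproduced.

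**Power within a level.** With d events, power = 1 − Φ(1.96 − √(d/4) × 0.4074).

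| Split | Events | Power in each level | Both significant | Exactly one | Neither |
|---|---|---|---|---|---|
| 50:50 | 127.5 / 127.5 | 63.3% / 63.3% | 40.1% | 46.5% | 13.5% |
| 60:40 | 153 / 102 | 71.2% / 53.9% | 38.4% | 48.4% | 13.3% |
| 70:30 | 178.5 / 76.5 | 77.7% / 42.9% | 33.4% | 53.9% | 12.7% |
| 80:20 | 204 / 51 | 82.9% / 30.7% | 25.4% | 62.7% | 11.9% |

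The two levels contain different subjects, so the probabilities multiply. At 50:50, exactly one is 2 × 0.633 × 0.367 = 0.465. At 80:20 it is 0.829 × 0.693 + 0.171 × 0.307 = 0.627. For a three-level factor the chance of a mixed result is 75% at equal thirds and 83% at 10/70/20.

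**All eight factors.** Simulation used 317 subjects, a cut at event 255, a uniform HR and 2,000 trials per scenario. Splits were even, moderate or skewed, and factors independent or correlated. Within-subgroup tests were unstratified and no dropout was simulated.
- At least one factor split: 94-98% of trials.
- Factors split on average: 4.2-5.0 of 8.
- Only the six two-level factors, each at 50:50: at least one split in 76-83%.

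**Interaction tests under the same uniform effect.** The false-signal rate is 5% per factor by construction (simulated 4.6-7.2%). For at least one of eight independent tests it is 1 − 0.95⁸ = 33.7% (simulated 33-42%).

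**Power of an interaction test.** SE of the log ratio of HRs = √(4/d₁ + 4/d₂). The ratio needed for 80% power is exp(2.80 × SE).
- 50:50: SE = √(4/127.5 + 4/127.5) = 0.2505; ratio about 2.0.
- 80:20: SE = √(4/204 + 4/51) = 0.313; ratio about 2.4.

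**The case against.** Several stronger readings are tempting, and the documents do not support them.

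- A reader might infer that the plan judges subgroups by their p-values. It does not say so: the SAP sets no level, decision rule or claim for subgroups, each HR and CI is printed alongside, and the forest-plot note mentions no p-value.
- A reader might count 18 subgroups in two sets as 36 certain p-values. The adequate-size condition could remove small levels, which are the ones that push the figures up. The 76-83% result shows what remains without the three-level factors and with even splits.
- A reader might set 94-98% of trials against 5% per factor. Those are different units. Per factor it is 46-63% against 5%; per trial it is 94-98% against about 34%.
- A reader might add that, if the drug had no effect, some subgroup would often look significant. About 45% of trials would have one in either direction, but only about 23-24% would have one favouring KW-0761. Eight interaction tests would still give at least one false signal in about 34%, so there is little gain on that ground.
- Not every subgroup is underpowered: a level holding 80% of events has 83% power.

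The factors are also not independent, since Protocol 3.2 defines SS by T4 plus B2 and so ties it to blood involvement. The correlated simulations stayed within 94-98%.

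The strongest remaining objection is that a CI crossing 1 says much the same as p>0.05, so deleting p-values leaves the pattern visible. That is fair. It is why the ratio of HRs must be shown and why removing p-values alone is not enough. Exploratory status limits what may be claimed, but it does not supply the missing comparison.

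**Conclusion.** The gap is real, and limited to exploratory reporting. The plan shows effects level by level and never estimates the difference between levels. With a uniform effect of the planned size, a single two-level factor would show one significant and one non-significant level in 46% of trials at 50:50, passing one half at about 65:35 and reaching 63% at 80:20. For an evenly split factor that is close to a coin toss; a misleading pattern becomes usual only over the whole set of factors.

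The per-factor figures rest on the planned HR and event count and on the stated splits. The whole-display figures rest on assumed prevalences and the simplified simulation above. The primary PFS test and the Sidak-adjusted key secondary tests do not depend on any of this. The change is worth making because it is cheap and answers the question the tables raise.

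**What to change.** In Tables 14.2.1.7.1 and 14.2.1.7.2, remove the within-subgroup log-rank p-values and keep each HR with its 95% CI. Figures 14.2.5 and 14.2.6 need no p-value removed.

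For each factor, in those tables and figures, add the treatment-by-factor interaction from a Cox model on all subjects in the analysis set. The model holds treatment, the factor, their interaction and the remaining stratification factors. Report the ratio of HRs with 95% CI and the interaction p-value; for region and race, report the pairwise ratios with one overall p-value. State in SAP 6.11.2.7 that these results are exploratory and unadjusted for multiplicity.

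The cost is one Cox model per factor in each analysis set (8 × 2 = 16) and a shell edit. No data, sample size or alpha changes. The drawback is low power: 80% power needs a ratio of HRs of about 2.0 at 50:50 and 2.4 at 80:20. The SAP should therefore say that a non-significant interaction is not evidence of a consistent effect.
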